## **STUDY POPULATION**

This study is a single-site clinical trial, to be performed at the Mirpur field site by the International Centre for Diarrheal Disease Research, Bangladesh (icddr,b). Mirpur is a densely populated part of the Dhaka metropolitan area with an estimated population of over 3.5 million. It consists of 16 wards with different low to middle income socio-economic groups of communities. The Mirpur site has been used extensively for many years with different vaccine trials and descriptive trials. The field office contains a participant waiting area, several examination rooms, a staff work and file room, a specimen processing area, archive room and a meeting room with 24 hours generator back-up. The area is well secured and has 24 hr security coverage and internet service. Socio- demographic information of the high risk population is available for this area. A geographic information system (GIS) is also available and is used for mapping of this area and identifying households and related information.

### **Study Population**

The study population will consist of healthy adults (18-45 years, inclusive), toddlers (2-4 years/24-59 months, inclusive), children (12-23 months, inclusive) and infants (6-11 months, inclusive) from the communities in the vicinity of the study clinic. Children, toddlers and infants will only be enrolled if their parents are fully informed about the study and provide consent for their children's participation.

### Eligibility

Participants will be in general good health. Final eligibility determination will depend on the results of the medical history, clinical examination, screening laboratory tests and fulfilment of all the inclusion and absence of any of the exclusion criteria, appropriate parental understanding of the study and completion of the consent process.

Investigators should always use good clinical judgment in considering a participant's overall fitness for inclusion in the trial. Some participants may not be appropriate for the study, even if they meet all inclusion/exclusion criteria. For instance, medical, occupational or other conditions present in the parents may make safety evaluations difficult or make toddlers and infants poor candidates for retention. All children, toddlers, and infants targeted for enrollment will need to have parents that can comprehend the purpose of the study and provide written or thumb print informed consent. In addition, the families should be resident in the area without plans to leave the study site during the course of the study.

### PART A: Adult Eligibility Criteria

### **Inclusion criteria**

- 1. Healthy male or female adults 18-45 years old, inclusive
- 2. General good health as determined by the screening evaluation no greater than 7days before enrollment and vaccination
- 3. Properly informed about the study, able to understand it and sign or thumb print the informed consent form
- 4. Available for the entire period of the study and reachable by study staff throughout the entire follow-up period
- 5. Females of childbearing potential who are willing to take a urine pregnancy test at screening and before the second vaccination. Pregnancy tests must be negative before each vaccination. Females of childbearing potential must agree to use an efficacious hormonal or barrier method of birth control during the study. Abstinence is also acceptable.
- 6. Informed Consent (signature or thumb print provided, with witness signature)

### **Exclusion criteria**

- 1. Presence of any significant known systemic disorder (cardiovascular, pulmonary, hepatic, renal, gastrointestinal, endocrine, immunological, dermatological, neurological, cancer or autoimmune disease) as determined by medical history and/or physical examination which would endanger the participant's health or is likely to result in non-conformance to the protocol.
- 2. History of congenital abdominal disorders, intussusception, abdominal surgery or any other congenital disorder or presence of a significant medical condition that in the opinion of the Investigator precludes participation in the study. Known or suspected impairment of immunological function based on medical history and physical examination. Clinical evidence of active gastrointestinal illness and acute disease at the time of enrollment
- 3. Screening positive with hepatitis B antigen and/or hepatitis C antibodies
- 4. Participation in research involving another investigational product (defined as receipt of investigational product) during the 30 days before planned date of first vaccination or concurrently participating in another clinical study at any time during the study period, in which the participant has been or will be exposed to an investigational or a non-investigational product
- 5. Clinically significant abnormalities in screening hematology or serum chemistry, as determined by the Study Physician
- 6. History of febrile illness within 48 hours prior to vaccination and fever at the time of immunization (fever is defined as a temperature ≥ 37.5°C (99.5°F) on axillary, oral, or tympanic measurement)
- 7. Prior receipt of any cholera (e.g., Dukarol, Shancol) or ETEC vaccine
- 8. Prior receipt of a blood transfusion or blood products, including immunoglobulins
- 9. Evidence of current illicit drug use or drug dependence
- 10. Current use of iron or zinc supplements within the past 7 days; current use of antacids (H2 blockers, omeprazole, OTC agents) or immunosuppressive drug
- 11. Any condition which, in the opinion of the investigator, might jeopardize the safety of study participants or interfere with the evaluation of the study objectives
- 12. Receipt of antimicrobial drugs for any reason within 14 days before vaccination
- 13. History of diarrhea during the 7 days before vaccination (see protocol definition of diarrhea)
- 14. Culture positive for ETEC, Shigella, V. Cholerae or Salmonella within 7 days before vaccination.
- 15. Acute disease at the time of enrollment or 3 days prior to enrollment
- 16. History of chronic administration (defined as more than 14 days) of immunosuppressant medications, including corticosteroids.

# PARTS B, C, and D: Children, Toddler, and Infant Eligibility Criteria

Fulfilment of all of the following criteria is required to accept a participant for Parts B, C or D in the study:

# **Inclusion Criteria**

- 1. Healthy male or female infants/toddlers/children ages:
  - a. Part B:  $\geq$ 24 and  $\leq$ 59 months old at the time of enrollment
  - b. Part C:  $\geq 12$  and  $\leq 24$  months old at the time of enrollment
  - c. Part D:  $\geq 6$  and < 12 months at the time of enrollment
- 2. General good health as determined by the screening evaluation no greater than 7 days before enrollment and vaccination
- 3. Parent properly informed about the study, able to understand it and sign or thumb print the informed consent form
- 4. Parent and child available for the entire study period of the study and reachable by study staff throughout the entire follow-up period
- 5. Informed Consent (signature or thumb of parent, with signature of witness, provided)

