# Methods:

This is a single site, Phase I/II, double-blind, randomized, placebo-controlled, dose-escalation, age-descending study that will first test the vaccine with and without dmLT in healthy adults, and then move sequentially into toddlers (24-59 months old), younger children (12-23 months old) and infants (6-11 months old). The study is designed as 4 parts, one for each of the four age-groups. All participants will receive two oral doses of ETVAX with or without dmLT adjuvant or placebo, with different vaccine dose levels assessed within each age-group. Before moving to higher dose levels, available safety data will be evaluated and reviewed by an Independent Protocol Safety Team (IPST) comprised of three independent safety monitors, who will review available safety data through Day 3 after the second immunization to make the recommendation to the Sponsor whether to proceed with the initiation of the next dose cohort in that same age group. Independent safety monitors will be individuals not associated with study operations and who have clinical trials and infectious disease experience. Before moving to the next lower age group, the icddr,b Data Safety Monitoring Board (DSMB) will review all

available safety data through Day 3 after the second immunization to make the recommendation to the Sponsor whether to proceed with initiation of the first dose cohort in an age group.

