### PART B: Toddlers (2-4 years/24-59 months, inclusive)

The second part (Part B) will enroll a total of 150 toddlers (90 vaccinees and 60 placebos), age 2-4 years (24-59 months, inclusive) into six separate cohorts to be recruited step-wise. The first cohort (B1) will include 25 toddlers, randomized to receive two administrations of ETVAX at /4 dose (15 children) or placebo (10 children). The second cohort (B2) will include 25 toddlers, randomized to receive two administrations of ETVAX alone at /2 dose (15 children) or placebo (10 children). The third cohort (B3) will include 25 toddlers, randomized to receive two administrations of ETVAX alone at full dose (15 children) or placebo (10 children). The fourth cohort (B4) will include 25 toddlers, randomized to receive two administrations of ETVAX at the highest safe dose (either the full dose, /2 dose, or /4 dose) together with 2.5 ug dmLT (15 children) or placebo (10 children). The fifth cohort (B5) will include 25 toddlers, randomized to receive two administrations of ETVAX at the highest safe dose (either the full dose, /2 dose, or /4 dose) together with 5 ug dmLT (15 children) or placebo (10 children). The sixth cohort (B6) will include 25 toddlers, randomized to receive two administrations of ETVAX at the highest safe dose (either the full dose, /2 dose, or /4 dose) together with 5 ug dmLT (15 children) or placebo (10 children). The sixth cohort (B6) will include 25 toddlers, randomized to receive two administrations of ETVAX at the highest safe dose (either the full dose, /2 dose, or /4 dose) together with 5 ug dmLT (15 children) or placebo (10 children). The sixth cohort (B6) will include 25 toddlers, randomized to receive two administrations of ETVAX at the highest safe dose (either the full dose, /2 dose, or /4 dose) together with 10 ug dmLT

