(15 children) or placebo (10 children). After each cohort, the IPST will review available safety data through Day 3 after the second immunization to make the recommendation to the Sponsor whether to proceed with the initiation of the next dose cohort. After Cohort B1, the DSMB will review available safety data through Day 3 after the second immunization to also make a recommendation to the Sponsor whether to proceed with the initiation of Cohort C1 (first dose cohort in 13-23 month old children). Given a planned sample size of groups of 15 toddlers each receiving varying doses of ETVAX with and without dmLT or placebo, Part B will have an approximately 90% chance of observing at least one serious adverse event of special interest for events that occur at a rate of 15%. The number and allocation of participants in Part B are shown below.

Cohort	Vaccine	dmLT	(N)	Schedule				
D1	 / 4 dose		15	$\mathbf{D} = 0.14 \pm 2$				
B1	Placebo		10	Day 0, $14 \pm 2$				
Independent Protocol Safety Team (IPST) reviews data through Day 3 after the second administration and makes a								
recommendation to the Sponsor whether to proceed to the initiation of Cohort B2; DSMB reviews the same dataset and makes a recommendation to the Sponsor whether to proceed to the initiation of Cohort C1.								
and makes a r		nsor whether to pro-		n of Cohort C1.				
B2	 / 2 dose		15	Day 0, $14 \pm 2$				
	Placebo		10					
			ation and makes a re	ecommendation to the Sponsor				
whether to pr	oceed to the initiation of Co	bhort B3.						
B3	Full dose		15	$Dot 0, 14 \pm 2$				
БЭ	Placebo		10	Day 0, $14 \pm 2$				
IPST reviews data through Day 3 after the second administration and makes a recommendation to the Sponsor of								
the highest safe dose and whether to proceed with the highest safe dose plus 2.5 ug of dmLT (Cohort B4).								
B4	Highest safe dose	2.5 ug	15	$D_{22} = 0.14 \pm 2$				
D4	Placebo		10	Day 0, $14 \pm 2$				
IPST reviews	data through Day 3 after th	e second administra	ation and makes a re	ecommendation to the Sponsor of				
the highest sa	fe dose and whether to proc	eed with the highes	st safe dose plus 5 u	g of dmLT (Cohort B5).				
D5	Highest safe dose	5 ug	15	$D_{11} = 0.14 \pm 2$				
B5	Placebo		10	Day 0, $14 \pm 2$				
IPST reviews data through Day 3 after the second administration and makes a recommendation to the Sponsor								

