#### PART B: Vaccine Dose and Participant Allocation By Cohort

If dmLT is not tolerated in this age-group, ETVAX will be tested alone in Parts C and D (i.e., cohorts C3, C4, D4 and D5 will be dropped). Note: Reactogenicity will be assessed through 7 days post dose 1 and dose 2; however, only data through Day 3 after the second dose is needed for all IPST and DSMB reviews.

PART C: Younger children (12-23 months, inclusive)

The third part will enroll a total of 100 participants. The first cohort (C1) will include 25 children, randomized to receive two administrations of ETVAX alone at ¼ dose (15 children) or placebo (10 children). The second cohort (C2) will include 25 children, randomized to receive two administrations of ETVAX alone at ½ dose (15 children) or placebo (10 children). The third cohort (C3) will include 25 children randomized to receive two administrations of ETVAX at the highest safe dose (either ½ or ¼ dose) together with 2.5 ug dmLT (15 children) or placebo (10 children). The fourth cohort (C4) will include 25 children randomized to receive two administrations of ETVAX at the dose evaluated in C4 (either ½ or ¼ dose) together with 5 ug dmLT (15 children) or placebo (10 children). After each cohort, the IPST will review available safety data through Day 3 after the second immunization to make the recommendation to the Sponsor whether to proceed with the initiation of the next dose cohort. After Cohort C1, the DSMB will review available safety data through Day 3 after the second immunization to the Sponsor whether to proceed with the second immunization to also make a recommendation to the Sponsor whether to proceed with

the initiation of Cohort D1 (first dose cohort in infants). Given a planned sample size of groups of 15 children each receiving varying doses of ETVAX with and without dmLT or placebo, Part C will have an approximately 90% chance of observing at least one serious adverse event or adverse event of special interest for events that occur at a rate of 15%. The number and allocation of participants in Part C are shown below.

Cohort	Vaccine	dmLT	(N)	Schedule	
Cl	 / 4 dose		15	$D_{1} = 0.14 \pm 2$	
C1	Placebo		10	Day 0, $14 \pm 2$	
whether to pr	data through Day 3 after the se oceed to the initiation of Cohor whether to proceed to the initiati	t C2; DSMB reviews th			
C2	 / 2 dose		15	$D_{\text{ext}} = 0.14 \pm 2$	
C2	Placebo		10	Day 0, $14 \pm 2$	

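### Inclusion criterion 1 lets a 24-month-old qualify for both Part B and Part C, against the 12-23 month definition of Part C elsewhere in the protocol

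*Protocol*

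**What the plan says.** The protocol states the age range for Part C in five places.

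- **Eligibility list for Parts B, C and D, Inclusion Criteria, item 1.** Part B is ≥24 and ≤59 months. Part C is ≥12 months with the upper limit "\leq 24$ months old at the time of enrollment". Part D is ≥6 months with the upper limit "< 12 months at the time of enrollment".
- **Methods summary.** The sequence after toddlers is "younger children (12-23 months old) and infants (6-11 months old".
- **Heading of the Part C design section.** "PART C: Younger children (12-23 months, inclusive".
- **Study Population.** "children (12-23 months, inclusive) and infants (6-11 months, inclusive".
- **Part B design text, on the review after cohort B1.** C1 is described as the "first dose cohort in 13-23 month old children".

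The Part B heading agrees with criterion 1a: "PART B: Toddlers (2-4 years/24-59 months, inclusive". No rule in the protocol assigns a child aged 24 months to one Part rather than the other.

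**The concern.** The eligibility list is what the site applies at screening, so an error there matters more than one in descriptive text. As written, a 24-month-old satisfies criterion 1a and criterion 1b.

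The overlap can arise in practice. After cohort B1, the same safety dataset goes to the IPST for the decision on B2 and to the DSMB for the decision on C1, so both Parts can be open at the one site. The choice of Part for a 24-month-old would then rest with study staff, and the Parts are not run alike. A child who meets criterion 1b at 24 months would also fall outside the Part C definition given in the design and population sections, so it would be unclear whether the enrollment is a protocol deviation.

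**Working it through.** No stated sample size or power figure is involved. The check intersects the age ranges, confirms the differences between the Parts, and sizes the overlap.

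**1. Intersection of the ranges in criterion 1**

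- Part B [24, 59] ∩ Part C [12, 24] = {24 months}: overlap.
- Part C [12, 24] ∩ Part D [6, 12) = empty.

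The list handles the C/D boundary with a strict bound and the B/C boundary without one. With 12-23 months for Part C, the B/C intersection is also empty and the three Parts cover 6-59 months without a gap.

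**2. What depends on the Part**

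| | Part B | Part C |
|---|---|---|
| ETVAX dose levels | 1/4, 1/2, full | 1/4, 1/2 |
| dmLT levels | 2.5, 5, 10 µg | 2.5, 5 µg |
| Buffer volume | 30 ml | 15 ml |
| Abdominal pain solicited | yes | no |

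Sources are the Part B and Part C design sections, the preparation instructions for each Part, and the list of solicited symptoms under Post Dose – Observation Period. One line for cohort C4 gives 30 ml of buffer for a vaccine-only arm that C4 does not have; all other Part C entries with a stated volume give 15 ml.

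**3. Size of the overlap**

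The protocol does not say whether age is exact or in completed months.

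- *Exact age:* the overlap is the single day on which the child turns 24 months. The expected number is close to zero.
- *Completed months:* criterion 1b spans 24 − 12 + 1 = 13 monthly ages, against 12 for the 12-23 month definition. If recruitment is uniform over those ages (assumption), the share aged 24 months is 1/13 = 7.7%.
  - All of Part C: 100/13 = 7.7 children.
  - Part C vaccinees: 4 cohorts × 15 = 60, and 60/13 = 4.6.
  - C1 vaccinees, whose data open the infant Part: 15/13 = 1.2.
  - In Part B the same month is 1 of 59 − 24 + 1 = 36 monthly ages.

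The 7.7% also supposes that 24-month-olds enter Part C at the same rate as every other age. Any sent to Part B instead would lower it.

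**The case against.** The strongest reply is that the intent is plain. Three places give 12-23 months, and the same list expresses 6-11 months as a strict bound below 12, so criterion 1b looks like a one-character slip. The text was also read from PDF by a program, so a misread sign cannot be fully excluded. The first point stands and is why this is an internal inconsistency rather than a flawed design. The second is possible but not established: the list shows both strict and non-strict signs, and a misread would not account for the 13-23 month phrase.

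The differences between the Parts are also narrower than the table may suggest. Part C's dose levels are all Part B levels too, and the two Parts share the clinical toxicity scale and the 12-59 month laboratory scale. How far the Parts actually recruit side by side cannot be checked, because the cohort schedule is in a figure that is not shown.

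A reader might infer three stronger things that the documents do not support:

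- **That randomisation is compromised.** Part was never randomised; it is set by age, and the dose cohort by sequential opening. Randomisation is within the cohort and is untouched.
- **That Part C loses its value as the safety step before infants.** The DSMB decision on D1 follows C1, where about 1 of 15 vaccinees would be affected even on the larger reading. The age-related problem the protocol reports is vomiting at 6-17 months with the first-generation vaccine. It shows no change in tolerability at 24 months.
- **That the 13-23 month phrase removes 12-month-olds.** It is a parenthetical description, not an eligibility rule.

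**Conclusion.** The point holds as an inconsistency in an operative eligibility rule. Criteria 1a and 1b overlap at 24 months, 1b contradicts the 12-23 month definition given three times elsewhere, and a third range appears in the Part B text. Where both Parts are open, the protocol leaves the assignment of a 24-month-old to staff discretion.

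The consequence is small. It ranges from near zero with exact age to about 7.7% of Part C under completed months and uniform recruitment; the protocol supplies neither the age convention nor an age distribution. The 7.7% is an upper scenario, not an expected value. There is no effect on the vaccine-placebo comparison within a cohort and no demonstrated effect on the step-down decisions. The case for correcting it is that eligibility should be unambiguous and the age strata disjoint.

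**What to change.** In criterion 1b, write ≥12 and <24 months. This matches the form already used for Part D and the 12-23 month definition elsewhere. In the Part B design text, change 13-23 month to 12-23 month.

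Keep age at enrollment as the reference point for Parts B, C and D alike. Moving Part C alone to age at first vaccination could replace the overlap with a gap. Screening may start up to 7 days before Day 0, and the Enrolled Population is defined by consent at screening. If enrollment is read that way, a child who turns 24 months between enrollment and Day 0 would be too young for Part B and too old for Part C.

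The cost is one amended criterion and one corrected phrase, with no added participants, visits or procedures.

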# **Exclusion Criteria**

- 1. Presence of any significant known systemic disorder (cardiovascular, pulmonary, hepatic, renal, gastrointestinal, endocrine, immunological, dermatological, neurological, cancer or autoimmune disease) as determined by medical history and/or physical examination which would endanger the participant's health or is likely to result in non-conformance to the protocol.
- 2. History of congenital abdominal disorders, intussusception, abdominal surgery or any other congenital disorder or presence of a significant medical condition that in the opinion of the Investigator precludes participation in the study. Known or suspected impairment of immunological function based on medical history and physical examination. Clinical evidence of active gastrointestinal illness and acute disease at the time of enrollment
- 3. Screening positive with hepatitis B antigen and/or hepatitis C antibodies
- 4. Participation in research involving another investigational product (defined as receipt of investigational product) during the 30 days before planned date of first vaccination or concurrently participating in another clinical study at any time during the study period, in which the participant has been or will be exposed to an investigational or a non-investigational product
- 5. Clinically significant abnormalities in screening hematology or serum chemistry, as determined by the Study Physician
- 6. History of febrile illness within 48 hours prior to vaccination and fever at the time of immunization (fever is defined as a temperature ≥ 37.5°C (99.5°F) on axillary, oral, or tympanic measurement)
- 7. Prior receipt of any cholera (e.g., Dukarol, Shancol) or ETEC vaccine
- 8. Prior receipt of a blood transfusion or blood products, including immunoglobulins
- 9. Current use of iron or zinc supplements within the past 7 days; current use of antacids (H2 blockers, omeprazole, OTC agents) or immunosuppressive drug
- 10. Any condition which, in the opinion of the investigator, might jeopardize the safety of study participants or interfere with the evaluation of the study objectives
- 11. Receipt of antimicrobial drugs for any reason within 14 days before vaccination
- 12. History of diarrhea during the 7 days before vaccination (see Protocol definition of diarrhea))
- 13. Culture positive for ETEC, *Shigella*, *V. cholerae*, *Salmonella* or Rotavirus (the latter for all children <5 years of age) within 7 days of vaccination
- 14. Acute disease at the time of enrollment or 3 days prior to enrollment
- 15. Known or suspected impairment of immunological function based on medical history and physical examination
- 16. Participant's parents/guardians not able, available or willing to accept active weekly follow-up by the study staff
- 17. History of chronic administration (defined as more than 14 days) of immunosuppressant medications, including corticosteroids. Infants on inhaled or topical steroids may be permitted to participate in the study
- 18. Any medical condition in the parentsinfant that, in the judgment of the investigator, would interfere with or serves as a contraindication to protocol adherence or a participant's parents' ability to give informed consent
- 19. Medically significant malnutrition, defined as moderate malnutrition (wt-for-ht z-score between -3.0 and -2.0) and severe malnutrition (wt-for-ht z-score <-3.0 or edema)

